2.1.4 Amendment 4 - 04/13/2017

No impact on the statistical analysis (recruitment period extended, status of the investigator and SAE reporting timeframe precised).

2.1.5 Amendment 5 - 10/26/2017

The purpose of this amendment is to update the patient information leaflet (emergency and post-inclusion) according to the new version of the Clottafact SPC (version 237119/1.0).

2.1.6 Amendment 6 - 11/24/2017

Administrative changes:

- Recruitment period extended until the date of the inclusion of the 470th patient if this inclusion occurs before June 30th, 2018 or until June 30th, 2018 considered as the end date for inclusions;
- The investigator can delegate completion of the CRFs to qualified and trained staff, but the signature of CRFs can only be delegated to physicians or midwives).

2.1.7 Amendment 7 - 03/06/2018

The purpose of this amendment is to update the patient information leaflet (emergency and post-inclusion) according to the new version of the Clotfact SPC (version February 2018).

2.2 CHANGES IN THE STATISTICAL ANALYSIS PLAN

Section	Protocol	SAP and rationale for changes
Analysed data sets	12.6. Protocol Deviations and Analysis Set "ITT set : all randomized patients"	SAP : "ITT set: all randomized patients considered as randomized patients (i.e. regardless of allocation errors) and having received at least one dose of the IMP." Rationale for change : this definition of the ITT set is the most commonly accepted. As specified in ICH E9, In some situations, it may be reasonable to eliminate from the set of all randomised subjects any subject who took no trial medication. The intention-to-treat principle would be preserved despite the exclusion of these patients provided, for example, that the decision of whether or not to begin treatment could not be influenced by knowledge of the assigned treatment. This assumption should hold in this double blind randomized trial.
	"Safety set : all patients who received at least one dose of IMP"	SAP : all patients receiving at least one dose of IMP and considered 'as treated' (i.e. assigned to the 'as treated' group regardless of randomization errors). If all randomized patients received their allocated treatment and if there is no randomization error, the 'as treated' analysis will be the same 'as randomized' analysis and Safety set will be the same than Intent-to-treat set.
Demographics and other baseline	"If the PP set represents less than 80% of the ITT set, demographic and	SAP : "Demographic and baseline characteristics of patients will be analysed on the ITT and PP

characteristics	baseline characteristics will also be presented on the PP set.”	set.”
Handling missing data	12.7. General Rules for Handling of Missing or Inconsistent Data “Concerning the primary efficacy endpoint, missing data (including incomplete dates) will be estimated as failures.”	
SAP: “No imputation of missing data will be proposed for the primary analysis of the primary endpoint. “
 
Rationale for change: There is no best method for handling missing data. The approach for handling missing data as recommended by the EMA guideline on missing data in confirmatory trials (EMA, 2010) should consider various missingness mechanisms along with subsequent analyses.
 
Three methods for handling missing data will be considered.
 
 - The method n°1 considers no replacement of missing data (which is considered as the primary method). - The method n°2 replaces missing data by failures regardless of the randomized treatment (which is considered as a sensitivity method). This method relies on strong assumptions corresponding to a particular MNAR missingness mechanism, and should thus not be envisaged in first place. - The method n°3 (which is considered as another sensitivity method) performs multiple imputations (MI) for missing data, assuming a MAR missingness mechanism. As there is no other post randomization assessment of the primary endpoint when this latter is missing, the multiple imputation process must be based on baseline and post randomization covariates other than intermediate assessments of the primary endpoint. Blinded simulations have shown that important prognostic factors (such as country) could not be fitted as the model could not converge. Hence, this method based on multiple imputations relies on a somewhat subjective choice of covariates and should not be considered as the primary one.
Primary Analysis	12.10.1.2. Primary analysis “The primary model analysis will be an exact logistic regression adjusting for treatment, centre, and baseline fibrinogen (categorized into three classes, ≤ 2 g/L,]2 g/L; 4g/L], > 4 g/L)”	SAP : The primary model of analysis will be a logistic regression to assess the association between a binary exposure variable treatment (variable “_trt”) and the binary outcome (variable “_resp”), adjusting for centre and baseline fibrinogen (variable “_b_fibrinogen”,

	12.10.1.2.2. Prognostic factors and covariates "Stratified center and baseline fibrinogen are considered as major prognostic factors for the primary outcome"	categorized into four classes (≤ 2 g/L,]2;3] g/L,]3,4] g/L, > 4 g/L). Rationale for change: as some centers would enroll too few patients, centres with small number of enrolled patients (< 20 patients) will be pooled into one group of centers. The interaction of adjusted variables with treatment effect will be estimated in another standard logistic regression models. If feasible, Influence of centre will be secondarily studied in a logistic regression model adjusting for center as an additional term.
Prognostic factors and covariates	12.10.1.2.2. Prognostic factors and covariates "Stratified center and baseline fibrinogen" "Possible administration of tranexamic acid defined as a binary covariate, (i.e. yes versus no) on the primary outcome during the trial will be evaluated in a separate model"	SAP: "Baseline fibrinogen will be considered as a major prognostic factor of the primary outcome. Baseline fibrinogen will be adjusted in the primary model as described above. As the linear relationship between baseline fibrinogen and the primary binary outcome (on the logit scale) is a priori ascertained, baseline fibrinogen will be categorized into four classes (≤ 2 g/L,]2;3] g/L,]3,4] g/L, > 4 g/L). Other possible prognostic factors will be considered as secondary and listed as follows : Other baseline covariates : -Center, -Tranexamic acid intake, -Lost of at least 2g/dl of haemoglobin (at the inclusion) compared to the reference level, -Heart rate ≥ 100 beats/min at the inclusion, -Measured/estimated total blood loss volume. Post-randomization covariates: -Fibrinogen concentrate as rescue therapy, -Tranexamic acid intake, -Fresh frozen plasma, -Administration of platelet units, -Haemostatic intervention by bakri balloon, -Haemostatic invasive procedures, -Transfer to intensive care unit, -Heart rate ≥ 100 beats/min " Rationale for change:: See primary analysis
Individual analyses of the composite primary endpoint	None	SAP: "[...] logistic regression adjusting for baseline fibrinogen value (categorized) will be used to compare Clottafact [®] and placebo groups." Each component of the primary endpoint will be analyzed separately according to the same logistic regression analyses planned for the primary endpoint.
Secondary analyses	"[...] all secondary efficacy variables will be compared between the 2groups using chi-square for categorical data and using t test for continuous quantitative data or other appropriate	SAP: "The change in plasma fibrinogen level, Hb and Ht will be analysed at H2, H6 and D2 following IMP administration with a Mixed Model for Repeated Measures (MMRM) comparing the Clottafact [®] group and placebo

	tests.”	group.”
Multiplicity	None	
SAP: “No multiplicity adjustment is necessary for the primary analysis as there is only one primary criterion and two arms compared. The 2-sided nominal alpha level of significance is set to 5%. Results for the two components of the composite primary endpoint will be individually examined without statistical hypothesis testing.
 
Secondary efficacy parameters will be tested for superiority at the 5% level of the Clotfact[®] arm, compared to the placebo arm. Secondary efficacy variables will be examined and may contribute to supportive information to the effectiveness. We distinguish two types of secondary endpoints: (1) Key secondary endpoints are defined as highly clinically relevant endpoints. Statistical methods for addressing multiplicity issues will be used to test sequentially key secondary endpoints (ie. Hochberg procedure); (2) other secondary endpoints will be analysed in an exploratory purpose.”

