12.3. Sample Size Determination

It is estimated that, in the control group, 42% of patients will fulfil the primary endpoint (unpublished data from the Pithagore cohort). With an expected percentage of patients in the Clottafact[®] treated group of 27%, the difference between the two groups will be of 15%. With a power (1-β) of 90%, a type I error (α) of 5% and a two-sided test (Z test, unpooled variance), a sample size of 206 patients per treatment group is needed.

The rate of drop-out is assumed to be approximately 5%. Therefore, 434 patients will be included in the study.

As there is some uncertainty about the test Z variance depending itself on the expected rates, the variance will be re-estimated in a blind way at 80% of the initially planned sample size (i.e. 80% of 412=326 evaluable patients or 348 patients with adjustment for a 5% dropout rate) and the sample size will be increased according to the new estimated variance so as to maintain the power to 90% while still considering the same originally planned difference in failure rates, i.e. 15%.

It can be shown that the possible increase in sample size with adjustment for a 5% dropout rate cannot exceed 50 additional patients. Therefore, the new sample size will not exceed 484 patients.“

Of note, as the sample size reassessment is performed in a blind way, i.e. based on an overall estimate of the overall failure rate, it is known to not inflate the type I error of the primary analysis. An additional rule for the reassessment of the sample size is as follows: only an increase (i.e. no decrease) in the sample size will be allowed at the blind interim analysis.

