1.4 TREATMENT

The investigational medicinal product (IMP) is either Clottafact® or placebo.

Injection of IMP must start as soon as possible and within 30 minutes following the start of prostaglandin infusion.

It is administered as a single-dose. A total volume of 200 mL of IMP (2 vials of 100 mL of reconstituted IMP) is injected to every patient.

Only one injection of IMP is performed to the patient throughout the study.

Following the administration of IMP, the therapeutic management is totally left to the discretion of the investigator. However, some concomitant treatments may be administered in accordance with the following recommendations:

- Fibrinogen concentrate as rescue therapy: if administered, it can't be administered:
 - within 60 minutes following the start of IMP administration,OR
 - before at least 2 units of packed red blood cells (RBCs) have been administered to the patient.
- Tranexamic acid:
 - The administration of tranexamic acid is allowed only after prostaglandin infusion has been decided.
 - Recommended dose: 1 g IV to be renewed once after 30 min.
- Transfusional strategy: in accordance with the following objectives:
 - Haemoglobin (Hb) ≥ 8 g /100 ml,
 - Prothrombin time $\geq 40\%$,
 - Platelets count $\geq 50\ 000/\text{mm}^3$,
 - Transfusions of RBC, FFP and platelets units can be performed before availability of laboratory results, when indicated.

- Hydroxyethylstarch (HES): maximum dose of 1.5 L during the first 24 hours.

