1.7 NUMBER OF INVESTIGATORS

The study was expected to be conducted in approximately 25 French investigational centers.

Each centre was expected to enrol a mean of 29 eligible patients.

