- requires the transfusion of at least 2 units of packed RBCs within 48 hours following the administration of IMP.

The reference Hb level is the most recent Hb value recorded during the third trimester of pregnancy.

Raw percentages of failures will be estimated within each treatment group (placebo or Clottafact®).

3.3.6.1.2 *Description of prognostic factors and covariates of the primary efficacy variable(s)*

Baseline fibrinogen will be considered as a major prognostic factor of the primary outcome. Baseline fibrinogen and centre (Centres with small number of enrolled patients (<20 patients) will be pooled arbitrary into one) will be adjusted in the primary model as described below. As the linear relationship between baseline fibrinogen and the primary binary outcome (on the logit scale) is a priori ascertained, baseline fibrinogen will be categorized into four classes (≤ 2 g/L,]2;3] g/L,]3,4] g/L, > 4 g/L).

Other possible prognostic factors will be considered secondarily and listed as follows:

- Other baseline covariates :
 - tranexamic acid intake (Yes/No),
 - lost of at least 2g/dl of haemoglobin (at V1) compared to the reference level (the last assessment during the third trimester),
 - heart rate at the inclusion (<100 beats/min vs. ≥ 100 beats/min)
 - measured/estimated total blood loss volume (<1000 ml vs. ≥ 1000 ml).

Raw percentages of failures will also be provided by centre, by tranexamic acid intake. (Yes versus No), by baseline fibrinogen (categorized into four classes: ≤ 2 g/L,]2;3] g/L,]3,4] g/L, > 4 g/L) and by other covariates levels identified above.

- Post-randomization covariates (within the 48 hours following IMP administration):
 - fibrinogen concentrate as rescue therapy,
 - tranexamic acid intake,

- administration of fresh frozen plasma,
- administration of platelet units,
- haemostatic intervention by bakri balloon,
- haemostatic invasive procedures,
- transfer to intensive care unit,
- heart rate \geq 100 beats/min.

Post-randomization covariates will be mainly used to implement the multiple imputation model for the primary analysis. Although partially confounded with the treatment effect, these post-randomization covariates will also be investigated to check whether they are treatment effect modifiers. Raw percentages of failures will be provided by post-randomization covariates levels.

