3.3.6.2.2 Model of analysis of the primary endpoint

The primary model of analysis will be a logistic regression to assess the association between a binary exposure variable treatment (variable “_trt”) and the binary outcome (variable “_resp”), adjusting for baseline fibrinogen (variable “_b_fibrinogen”, categorized into four classes (\leq 2 g/L,]2;3] g/L,]3,4] g/L, $>$ 4 g/L) and centre (see SAS code in §7.1). Missing data will be not imputed, assuming the missing completely at random (MCAR) assumption.

The treatment effect (odds ratio of failure) with its 95% confidence interval (95% CIs) will be provided by treatment group and tested at the 5% two-sided level of significance in this model.

Validity of the primary analysis: A graphical analysis of residuals will be done for verifying that assumptions for the primary analysis are met. If adjusting for centre effects lead to convergence issues or unstable estimates, centre effect will be ignored in the analysis.

3.3.6.2.3 *Sensitivity Analyses of the primary endpoint*

3.3.6.2.3.1 Primary sensitivity analysis (MAR assumption)

Assuming the missing at random (MAR) mechanism, multiple imputation (MI) approach by Fully Conditional Specification (FCS) will be used to handle missing data of the primary efficacy endpoint.

A stepwise logistic regression will be done to identify relevant covariates by a backward elimination analysis based on iterative maximum likelihood with the Newton-Raphson algorithm using a significance level of 0.2 to retain variables in the model. Only relevant covariates will be introduced in the MI process. The number of imputations needed will be verified with relative efficiency (RE) for the fully efficient imputation (in unit of variance) and by replicating sets of imputations checking whether the estimates are stable between imputation sets. With a little of missing information (10%), only a small number of imputations are necessary.

The final set of key covariates (referenced here below in the SAS syntax as “key_covariates_for_MI”, see §7.2 for SAS code) to be accounted for in the MI model in addition to treatment and categorized baseline fibrinogen will be defined before breaking the blind.

3.3.6.2.3.2 Secondary sensitivity analysis (MNAR assumption)

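### The MAR imputation model is fitted to all women without a red cell term, although only women with fewer than 2 recorded units can need imputing, so it imputes somewhat too many failures

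*SAP*

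**What the plan says.** The endpoint (SAP 1.10.1) is a composite. A woman fails if her Hb falls by at least 4 g/dL from the third-trimester reference, or if she receives at least 2 red cell units within 48 hours, or both. SAP 3.3.3 treats the endpoint as missing only when it cannot be evaluated, and discusses this in terms of a missing Hb value.

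SAP 3.3.6.2.3.1 makes multiple imputation under MAR the primary sensitivity analysis. On the source of its covariates, SAP 3.3.6.1.2 states: "Post-randomization covariates will be mainly used to implement the multiple imputation model for the primary analysis". The list, given there and in SAP 2.2, includes "Fibrinogen concentrate as rescue therapy, -Tranexamic acid intake, -Fresh frozen plasma, -Administration of platelet units", then balloon, invasive procedures, intensive care transfer and heart rate. Red cell units are not on it. Covariates are chosen by backward elimination "using a significance level of 0.2 to retain variables in the model", and the final set is to be fixed before unblinding. Code 7.2 then fits a single logistic model for the composite response, with no restriction by transfusion status.

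Two related statements matter. SAP 1.4 says that rescue fibrinogen is not to be given "before at least 2 units of packed red blood cells (RBCs) have been administered to the patient". On why imputation is not the primary method, SAP 2.2 says: "Blinded simulations have shown that important prognostic factors (such as country) could not be fitted as the model could not converge".

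**The concern.** A woman with 2 or more recorded units is a known failure whatever her Hb, so she never needs imputing. Everyone who is imputed belongs to the group with fewer than 2 units, where failure can come only through Hb and is therefore less frequent. A model fitted to all women with an observed endpoint also learns from the transfusion failures and carries their higher failure rate over to women who cannot be among them.

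In missing-data terms, missingness depends on an observed variable, the recorded transfusion status, which the model leaves out. MAR may hold given that variable, but it does not hold given the listed covariates alone. What is at stake is how well the designated primary sensitivity analysis does its job.

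**Working it through.** **The plan's own figures.** Protocol 12.3 assumes that "in the control group, 42% of patients will fulfil the primary endpoint", against 27% on active treatment. With unpooled variance, n = (1.960 + 1.282)² × (0.42×0.58 + 0.27×0.73) / 0.15² = 205.8, so 206 per arm. Then 412/0.95 gives 434. Both agree with the documents. The documents give no figure for the imputation model itself.

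**Inputs**
- Analysed women: 448 × (1 − 0.0155) = 441 (SAP 1.11).
- Overall failure rate F: 34.5% as planned (the mean of 42% and 27%). The re-estimated total of 470 gives 470 × 0.95/2 = 223.25 evaluable per arm. Solving the sample-size formula for the overall rate gives 42.7% or 57.3%. SAP 1.11 says only that the rate was higher than expected, so both roots are kept.
- Share with at least 2 units, R: not in the documents; assumed 10 to 25%.
- Share given rescue fibrinogen, q: not in the documents; assumed 0 to R, all among women with at least 2 units.
- Missing endpoints: assumed 22, about 5% of 441, from the planned drop-out rate.
- Transfusion records assumed complete when Hb is missing.

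**Closed form.** A model that sees rescue but not red cells predicts failure in non-rescued women at (F − q)/(1 − q). The rate wanted, in women with fewer than 2 units, is (F − R)/(1 − R). With R = 15% and q = 5%:

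| F | Model | Fewer than 2 units | Excess, points | Extra failures in 22 |
|---|---|---|---|---|
| 34.5% | 31.1% | 22.9% | 8.1 | 1.8 |
| 42.7% | 39.7% | 32.6% | 7.1 | 1.6 |
| 57.3% | 55.1% | 49.8% | 5.3 | 1.2 |

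Over all the inputs above, the excess runs from 0 points (q = R: every woman with 2 or more units was rescued) to 21.8 points (F = 34.5%, R = 25%, q = 0). In 22 women that is 0 to 4.8 failures.

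**Simulation with the eight listed covariates.** 300 data sets of 441 women per setting, 42% failure, about 22 missing, at least 2 units in 10 to 25%, rescue in 35% of those, Wald elimination at 0.2. Imputed failure rates were 40, 38, 37 and 35%, against true rates of 36, 33, 29 and 24%: an excess of 4, 5, 8 and 11 points. Fitting only below 2 units gave 37, 32, 29 and 24%.

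**Simulation of the role of rescue fibrinogen.** 300 data sets, true rate 46.1% in the missing women. Imputed rates:
- neither rescue nor red cells: 55.2%
- rescue: 51.4%
- rescue plus fresh frozen plasma: 49.6%
- fitted only below 2 units: 45.8%

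Across simulations with different assumed inputs the excess was about 4 to 12 points, and the restricted fit came within 2 points of the truth.

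**Effect on the odds ratio.** Take 220.5 women per arm with failure rates of 34.5% and 49.5% (42% overall, plus and minus 7.5 points), that is 76.07 and 109.15 failures. The odds ratio is (76.07/144.43)/(109.15/111.35) = 0.537. Adding 1.25 false failures to each arm gives (77.32/143.18)/(110.40/110.10) = 0.539. The log odds ratio moves by 0.002, against a standard error of √(1/76.07 + 1/144.43 + 1/109.15 + 1/111.35) = 0.195.

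**The case against.** **For the plan.** SAP 2.2 gives a reason that would exclude red cell units: imputation covariates must not be intermediate assessments of the endpoint, and red cells are one of its components. Plasma, platelets, invasive procedures and intensive care transfer are on the list and partly stand in for transfusion. The list is one of candidates. SAP 3.3.3 fills some missing Hb values from non-study measurements, which reduces missingness. The missing-as-failure analysis already covers the extreme of too many imputed failures. A woman lost before 48 hours with 0 or 1 recorded units could still have failed by transfusion.

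Most of this stands as mitigation. The stated reason does not remove the problem, because the remedy adds no covariate: it restricts the fit to the women who can need imputing. The proxies narrow the excess without closing it. The last point is sound and calls for a separate rule.

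**A stronger reading.** A reader might infer from SAP 1.4 that rescue fibrinogen predicts failure perfectly, that the imputation model therefore has no finite fit, and that this produces the excess failures and the non-convergence reported in SAP 2.2. The documents do not support that chain:
- SAP 1.4 presents the rule as a recommendation, with management left to the investigator, and joins its two conditions by 'or'. Protocol 7.2 describes rescue after red cells but inside the 60 minutes. These passages must be reconciled. In simulation, once 1% of women below 2 units were also rescued, perfect prediction remained in only 17% of data sets.
- Rescue is a candidate, and SAP 3.3.6.2.3.1 does not name the test used for elimination. Under a Wald test a perfect predictor would be dropped.
- Even under perfect prediction only the rescue coefficient diverges. Fitted probabilities for non-rescued women stay finite.
- Keeping rescue in the model reduced the excess (55.2% to 51.4%).
- SAP 2.2 attributes the non-convergence to factors such as country, not to rescue.

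**Conclusion.** The point holds as a modest bias in a sensitivity analysis. The imputation model ignores the one recorded fact that determines who can have a missing endpoint, and so imputes failure about 4 to 12 points too often under assumed inputs, or roughly 1 to 2.5 women in 22. The effect on the odds ratio is small: a shift of about 0.01 or less on the log scale, against a standard error of about 0.2, if missing endpoints are balanced between arms. The primary analysis is unaffected.

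The size rests on assumed values for the share transfused, the share rescued and the number missing, and on transfusion records being complete when Hb is missing. If those records are missing too, the argument weakens. The correction is worth making because it is cheap, not because it is likely to change a conclusion.

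Two clerical slips sit alongside. SAP 2.2 names country as a factor, whereas SAP 1.7 says: "The study was expected to be conducted in approximately 25 French investigational centers". And code 7.2 puts centre in the imputation model, while the text of 3.3.6.2.3.1 names only treatment and categorised fibrinogen besides the key covariates.

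**What to change.** In SAP 3.3.6.2.3.1 and code 7.2:
- Select covariates, fit and impute only in women with fewer than 2 red cell units recorded within 48 hours.
- Append the remaining women, all known failures, to each of the 100 imputed data sets, and run the primary model on everyone.
- State separately how women with an incomplete 48-hour transfusion record are handled.
- Do not add an indicator for 2 or more units as a covariate in the unrestricted model; it would itself predict failure perfectly.

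Rescue fibrinogen needs no special treatment. If the literal rule in SAP 1.4 is followed, it is nearly constant in the restricted set and drops out. Align text and code on centre, and correct the country sentence.

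The cost is a short SAP edit, a restriction and an append step in the code, all before unblinding, when the covariate set is to be fixed anyway. The imputation model also uses fewer women: about 66 fewer if R is 15% (0.15 × 441).
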